**Table 7-1: Minimum and maximum LCM dose during the Treatment Period**

Formulation	Minimum LCM dose	Maximum LCM dose
Oral solution (pediatric subjects <50 kg)	4mg/kg/day	12mg/kg/day
Tablets (pediatric subjects $\geq 50$ kg)	200mg/day	600mg/day
Tablets (adult subjects)	200mg/day	800mg/day

LCM=lacosamide

The LCM dose may be adjusted at the investigator's discretion after the subject receives the first dose of LCM in the study. Baseline failures must complete Week 1 of dosing before LCM may be increased or decreased. The maximum dose for pediatric subjects weighing <50kg is 12mg/kg/day (oral solution). The maximum dose for pediatric subjects weighing  $\geq 50$ kg is 600mg/day (tablets) and for adult subjects is 800mg/day (tablets).

A clinic visit (scheduled or unscheduled) is required if:

- The dose is increased for the first time to any dose above 10mg/kg/day for pediatric subjects weighing <50kg. One week after the first time the dose is increased, an unscheduled telephone contact must be conducted to ensure that the dose is well tolerated.
- The dose is increased for the first time to any dose above LCM 400mg/day for all adult subjects or pediatric subjects weighing  $\geq 50$ kg. One week after the first time the dose is increased, an unscheduled telephone contact must be conducted to ensure that the dose is well tolerated.

Subjects withdrawing from the study must complete the ET Visit and (if they do not proceed with commercially available LCM) an up to 4-week taper followed by an End of Taper Visit (see taper schedule, Table 7-2). Following the End of Taper Visit, there will be a 30-day

Safety Follow-Up Period. The Safety Follow-Up Period consists of a clinic visit 2 weeks after the End of Taper Visit followed by a Safety Follow-Up telephone contact 30 days after the last dose of study drug. A slow taper is permitted if medically necessary. Whenever possible, these cases should be discussed with the Medical Monitor prior to withdrawing the subject from the study. In case of an emergency, a faster taper is permitted after discussion with the Medical Monitor, whenever possible.

At the completion of the Treatment Period, investigators should discuss treatment options with the subject and/or their parent(s)/legal representative(s) to best manage the subject's epilepsy. Taper of LCM may not be required for some subjects who complete the study depending on the treatment option selected by the investigator in consultation with the subject and/or parent(s)/legal representative(s).

Subjects completing the Treatment Period and not continuing with commercially available LCM must complete the Termination Visit and also undergo taper, followed by an End of Taper Visit (see taper schedule, [Table 7-2](#)), and a 30-day Safety Follow-Up Period.

The following table summarizes the recommended LCM dose taper:

**Table 7-2: Lacosamide dosing for subjects requiring taper**

Dose of LCM at ET/Termination Visit a	LCM taper schedule			
	Week 1	Week 2	Week 3	Week 4
11 or 12mg/kg/day	9mg/kg/day	6mg/kg/day	4mg/kg/day	2mg/kg/day
9 or 10mg/kg/day	8mg/kg/day	6mg/kg/day	4mg/kg/day	2mg/kg/day
7 or 8mg/kg/day	6mg/kg/day	4mg/kg/day	2mg/kg/day	NA
5 or 6mg/kg/day	4mg/kg/day	2mg/kg/day	NA	NA
4mg/kg/day	2mg/kg/day	NA	NA	NA
800mg/day	600mg/day	400mg/day	200mg/day	100mg/day
700mg/day	500mg/day	300mg/day	200mg/day	100mg/day
600mg/day	500mg/day	300mg/day	200mg/day	100mg/day
500mg/day	400mg/day	300mg/day	200mg/day	100mg/day
400mg/day	300mg/day	200mg/day	100mg/day	NA
300mg/day	200mg/day	100mg/day	NA	NA
200mg/day	100mg/day	NA	NA	NA

ET=early termination; LCM=lacosamide; NA=not applicable

Note: The oral solution is dosed as mg/kg/day and tablets are dosed as mg/day.

aSubjects will begin taper on ET/Termination Visit.

### 7.3 Packaging

Lacosamide (tablets and oral solution) is manufactured, packaged, and labeled according to Good Manufacturing Practice guidelines and applicable laws or regulations. The IMP is suitably packaged in such a way as to protect the IMP from deterioration during transport and

storage. Oral solution will be packaged in amber polyethylene terephthalate bottles. Tablets will be supplied in high-density polyethylene bottles with child proof polypropylene screw caps.

#### **7.4 Labeling**

Clinical drug supplies will be labeled in accordance with the current International Council for Harmonisation (ICH) guidelines on Good Clinical Practice (GCP) and Good Manufacturing Practice and will include any locally required statements. If necessary, labels will be translated into the local language.

#### **7.5 Handling and storage requirements**

The investigator (or designee) is responsible for the safe and proper storage of IMP at the site. Investigational medicinal product stored by the investigator is to be kept in a secured area with limited access according to the storage conditions mentioned on the label.

Appropriate storage conditions must be ensured by controlling the temperature (eg, room, refrigeration unit) or by completion of a temperature log (showing actual and minimum/maximum temperatures reached over the time interval) in accordance with local requirements on a regular basis.

In case an out-of-range temperature is noted, it must be immediately reported as per the instructions contained in the IMP Handling Manual.

The investigator (or designee) will instruct the subject to store the IMP following the instructions on the label.

#### **7.6 Drug accountability**

A Drug Accountability Form will be used to record IMP dispensing and return information on a by-subject basis and will serve as source documentation during the course of the study. Details of any IMP lost, damaged (due to breakage or wastage), not used, partially used, disposed of at the study site, or returned to the sponsor's designee must also be recorded on the appropriate forms. All supplies and pharmacy documentation must be made available throughout the study for UCB (or designee) to review.

The investigator (or designee) is responsible for retaining all used, unused, and partially used containers of IMP until returned or destroyed.

The investigator may assign some of the investigator's duties for drug accountability at the study site to an appropriate pharmacist/designee.

The investigator must ensure that the IMP is used only in accordance with the protocol.

Periodically, and/or after completion of the clinical phase of the study, all used (including empty containers)/partially used, unused, damaged, and/or expired IMP must be reconciled and either destroyed at the site according to local laws, regulations, and UCB Standard Operating Procedures (SOPs) or returned to UCB (or designee). Investigational medicinal product intended for the study cannot be used for any other purpose than that described in this protocol.

## 7.7 Procedures for monitoring subject compliance

At each visit after IMP is dispensed, subjects must return all unused IMP and empty IMP bottles. Drug accountability must be completed in the subject's presence in order to obtain explanations regarding discrepancies in compliance with the dosing regimen. Drug accountability must be recorded on the Drug Accountability Form.

If a subject is found to be persistently noncompliant (defined as less than 75% or more than 125% compliant with the dosage schedule), the sponsor, in conjunction with the investigator, will make a decision as to whether the subject should be withdrawn from the study.

Timely completion of the subject diary is essential for evaluation of safety and efficacy. Subject diary completion, including AED usage, will be evaluated at each clinic visit and telephone contact. Sites are encouraged to call subjects to inquire about their diary completion. Investigators should advise subjects and/or caregivers about the importance of reporting non-PGTCS.

## 7.8 Concomitant medication(s)/treatment(s)

All concomitant medication and treatment must be recorded in the appropriate study documents (eg, eCRF and source document).

### 7.8.1 Permitted concomitant treatments (medications and therapies)

Female subjects not surgically sterile or 2 years postmenopausal should practice 1 highly effective method of contraception (according to ICH guidance, defined as those that result in a failure rate of <1% per year when used consistently and correctly), unless sexually abstinent, for the duration of the study. Recommended contraception methods for subjects on enzyme-inducing antiepileptic drugs (EI-AEDs) or not on EI-AEDs are detailed in Section 16.7. Subjects on EI-AEDs who do not use one of the highly effective contraception methods recommended for this group may practice 2 combined methods of contraception (ie, combined hormonal contraception plus barrier method with spermicidal agent).

The initiation of felbamate treatment while participating in EP0012 is prohibited.

The use of neuroleptics except for clozapine is allowed. The use of barbiturates and narcotic analgesics is also allowed. Stable use of benzodiazepines is allowed as concomitant AEDs, but intermittent use is only allowed as rescue medication for epilepsy indications (maximum 1 dose per week).

During the Treatment Period, new concomitant AEDs may be introduced, if the concomitant medication has been approved by the regulatory authority for the respective patient indication in the subject's country. For example, a new AED may be added when the subject has not optimally or adequately responded (lack of efficacy or tolerance) to LCM. Concomitant AEDs may be carefully tapered and discontinued to achieve LCM monotherapy, if clinically appropriate. The Medical Monitor must be consulted prior to initiation of concomitant AED withdrawal.

## 7.8.2 Prohibited concomitant treatments (medications and therapies)

The following medications/therapies are prohibited during the course of this study:

- Clozapine
- MAO-A inhibitors
- Vigabatrin

Therapy that becomes necessary (in the investigator's opinion) during the course of the study must not be refused to a subject, even if described above as a therapy that is expressly not permitted. In cases where this occurs but withdrawal criteria have not been met, the advisability of the subject's continuation in the study must be discussed between the Medical Monitor and the investigator.

## 7.9 Blinding

This is an open-label study; there will be no blinding.

## 7.10 Randomization and numbering of subjects

This is an open-label study and subjects will not be randomized to any treatment groups. The unique identification number assigned to subjects during the previous SP0982 study will be used to identify subjects and to maintain subject confidentiality throughout the current study. An IRT will be used to assign the applicable LCM treatment. Further instructions will be provided in the IRT manual.

# 8 STUDY PROCEDURES BY VISIT

Prior to any study activities, the subject or legal representative will be asked to read and sign an Informed Consent form that has been approved by an IRB/IEC and that complies with regulatory requirements. The subject or legal representative will be given adequate time to consider any information concerning the study, given to them by the investigator or designee. As part of the informed consent procedure, the subject or legal representative will be given the opportunity to ask the investigator any questions regarding potential risks and benefits of participation in the study. Additionally, if applicable (according to the subject's age and local requirements), the subject will sign an IRB/IEC Assent form.

All visits occur at the end of the respective week in the study and a window of  $\pm 7$  days relative to Visit 1 is applicable for all visits and telephone contacts. Subjects will have a Telephone Contact every 8 weeks if no clinic visit is scheduled.

A detailed schedule of study assessments for treatment Years 1 to 2 is provided in [Table 5-1](#), for treatment Years 3 to 5 in [Table 5-2](#), [Table 5-3](#) and for the Taper Period and Safety Follow-Up Period in [Table 5-4](#).

## 8.1 Treatment Period

### 8.1.1 Visit 1 (Week 0)

The following tasks and procedures are to be performed at this visit (for subjects who have completed SP0982, assessments marked [\*] should have already been completed during the last visit of the previous protocol and do not need to be repeated at Visit 1; for eligible

Baseline failures from SP0982, a full Visit 1 is required including all scheduled tasks and procedures). Tapered subjects from SP0982 will enter EP0012 for the Safety Follow-Up only and will be withdrawn at Visit 1 once Visit 1 assessments have been performed. Details of the Safety Follow-Up are provided in [Section 8.4.2](#) and [Section 8.4.3](#).

- Written Informed Consent/Assent
- Inclusion/exclusion criteria
- Subject identification card dispensed
- Concomitant medications and AEDs\*
- Medical history/epilepsy history update
- Physical examination (complete)\*
- Neurological examination (complete)\*
- ECG (12-lead) assessment\*
- Vital signs (pulse rate, BP) including orthostatic assessments\*
- Body weight and height\*
- Tanner staging (will be performed only for subjects who are pubescent at Visit 1 or who enter puberty during the course of the study)
- C-SSRS assessment (for subjects  $\geq 6$  years of age)
- Blood and urine samples for clinical laboratory assessments (includes hematology, chemistry, endocrinology for subjects  $< 18$  years of age at Visit 1, urinalysis, and a serum pregnancy test [for women of childbearing potential]).\* Baseline failures from SP0982 may have an additional urine pregnancy test at V1 of EP0012, at the investigator's discretion.
- Contact IRT
- Dispense subject diary
- Dispense LCM
- Assess withdrawal criteria\*
- AE reporting\*
- EQ-5D-3L (for subjects  $\geq 12$  years of age)
- QOLIE-31-P (for subjects  $\geq 18$  years of age)/PedsQL (for subjects  $< 18$  years of age)
- Achenbach CBCL for subjects  $< 18$  years of age
- BRIEF for subjects  $< 18$  years of age
- Healthcare resource use\*
- Work/school days lost due to epilepsy\*

- Days with help from a caregiver due to epilepsy\*

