Note: Visit 6, Visit 7 and Visit 10 (\*\*) assessments will not be performed according to Protocol Amendment 3.

a The duration of the Treatment Period will continue for at least 2 years and vary by subject age group and is defined in Section 5.1.1.

b Unscheduled Visits may be performed at any time after Visit 1, as clinic visits or telephone contacts, at the discretion of the investigator. In addition to the required assessments listed above, depending on the type of visit (clinic or telephone), further assessments can be completed as needed and may include ECG, laboratory tests, etc. The C-SSRS must be performed if the Unscheduled Visit is due to an AE.

c A window of ±7 days relative to Visit 1 is applicable for all visits and telephone contacts. Subjects will have a Telephone Contact every 8 weeks if no clinic visit is scheduled.

d Telephone contacts are required every 8 weeks including Week 30 and Week 38 during the study, except during weeks in which a clinic visit is planned (eg, Week 62). Therefore, telephone contacts in Year 2 are scheduled for Week 54, Week 70, Week 78, and Week 86.

e An ET Visit must be completed for all subjects who prematurely discontinue from the study. This will be followed by LCM taper, an End of Taper Visit, and a Safety Follow-Up Period; see Table 5-4. For subjects who continue on commercial LCM, the early Termination Visit is the last visit in the study.

- f A Termination Visit must be completed for all subjects who complete the study. This can be combined with Visit 17 if appropriate (see [Table 5-2](#)). For subjects who will not continue on LCM, this visit will be followed by LCM taper, an End of Taper Visit, and a Safety Follow-Up Period; see [Table 5-4](#). For subjects who continue on LCM, the Termination Visit is the last visit in the study.
- g The complete physical examination will include cardiac and respiratory function via auscultation and review of all body systems.
- h The brief physical examination will include review of the following body systems: cardiovascular, pulmonary, abdominal (hepato-gastrointestinal), and dermatologic.
- i The complete neurological examination will include selected assessment of mental status, sensory systems, motor functions, cranial nerves, reflexes, and coordination/cerebellar function.

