### 6.3 Withdrawal criteria

Subjects are free to withdraw from the study at any time, without prejudice to their continued care. Investigators should contact the Medical Monitor whenever possible to discuss the withdrawal of a subject in advance. All subjects discontinuing treatment with LCM for any reason should taper as described in Section 7.2. All subjects who withdraw due to an AE must be followed until resolution of the event or until the event is considered stable.

Subjects **must** be withdrawn from the study if any of the following events occur:

1. Tapered subjects from SP0982 who enter EP0012 after the 125th event will be withdrawn at the enrollment visit and enter directly into the Safety Follow-Up Period without and ET Visit being performed in EP0012.
2. The subject develops second or third degree atrioventricular (AV) block.
3. The subject becomes pregnant, as evidenced by a positive pregnancy test.
4. The sponsor or a regulatory agency requests withdrawal of the subject.
5. The subject is unwilling or unable to continue, or the legal representative is unwilling or unable to allow the subject to continue in the study.
6. In the case of liver function test (LFT) results of transaminases (ALT and/or aspartate AST)  $\geq 3x$  ULN to  $< 5x$ ULN and total bilirubin  $\geq 2x$ ULN or transaminases (AST and/or ALT)  $\geq 5x$ ULN, LCM must be immediately discontinued, and the subject withdrawn from the study. The LFTs will be repeated as soon as possible, and in no case more than 1 week later.
7. Subject  $\geq 6$  years of age has actual suicidal ideation since last visit as indicated by a positive response "Yes" to either Question 4 or Question 5 of the "Since Last Visit" version of the C-SSRS. The subject should be referred immediately to a Mental Healthcare Professional and must be withdrawn from the study.
8. Subject is unable to tolerate at least the minimum LCM target dose of 4mg/kg/day (oral solution) or 200mg/day (tablets).

Subjects **may** be withdrawn from the study if any of the following events occur:

- The subject requires a medication that is not permitted (see Section 7.8).
- The subject is unable to manage the completion of the diary, demonstrates a questionable diary, or is noncompliant with the study procedures or medications in the opinion of the investigator.

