#### 7.2.1 Treatment Period

At Visit 1, subjects who completed SP0982 will start on a dose of LCM 10mg/kg/day for pediatric subjects weighing <30kg, LCM 8mg/kg/day for pediatric subjects weighing  $\geq 30$ kg to <50kg, and LCM 400mg/day (200mg bid) for adult subjects ( $\geq 18$  years of age) or pediatric subjects weighing  $\geq 50$ kg. Subjects who are eligible Baseline failures from SP0982 will start at Visit 1 on a dose of LCM 2mg/kg/day for pediatric subjects weighing <50kg, and LCM 100mg/day (50mg bid) for adult subjects ( $\geq 18$  years of age) or pediatric subjects weighing  $\geq 50$ kg.

Baseline failures are required to complete Week 1 of dosing before LCM dosing flexibility based on tolerability is allowed. Investigators will assess whether a subject would tolerate a further LCM dose increase or whether a subject should hold the dose for a longer duration. There is no limit to the number of back titration steps or dose holds allowed and all are at the Investigator's discretion; however, subjects must achieve the minimum LCM target dose of 4mg/kg/day (oral solution) or 200mg/day (tablets).

Subjects who tapered in SP0982 after the 125th event will enroll at Visit 1 and proceed directly to the Safety Follow-up Period without receiving LCM.

At any time during the course of the study if it becomes apparent that a subject is unable to attain at least this minimum dose of 4mg/kg/day (oral solution) or 200mg/day (tablets), then the subject must enter the Taper Period and be withdrawn from the study.

During EP0012, investigators will be allowed to increase or decrease the dose of LCM to optimize tolerability and seizure reduction. Lacosamide doses may be increased or decreased in steps of no more than 2mg/kg/day (oral solution) or 100mg/day (tablets). Subjects must remain on the dose for  $\geq 7$  days before a subsequent dose escalation.

Table 7-1 provides the minimum and maximum LCM dose during the Treatment Period.

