### **8.1.2 Visits 2 to 8 (Weeks 2 to 46, Year 1, excluding Visit 6 and Visit 7)**

The following tasks and procedures are to be performed at these visits:

- Concomitant medications and AEDs
- Physical examination (brief, Visit 2, 3, 4, and 5; complete, Visit 8)
- Neurological examination (brief, Visit 2, 3, 4, and 5; complete, Visit 8)
- ECG (12-lead) assessment (Visit 2, 4, and 8 only)
- Vital signs (pulse rate, BP) including orthostatic assessments
- Body weight (Visit 4, and 8 only)
- Tanner staging (will be performed only for subjects who are pubescent at Visit 1 or who enter puberty during the course of the study) (Visit 8 only)
- C-SSRS assessment (for subjects  $\geq 6$  years of age)
- Blood and urine samples for clinical laboratory assessments (includes hematology, chemistry, and urinalysis) [Visit 2, 5, and 8 only], and a urine pregnancy test [for women of childbearing potential]
- Contact IRT
- Dispense subject diary
- Subject diary return/review
- Dispense LCM
- LCM review/return
- Assess withdrawal criteria
- AE reporting
- EQ-5D-3L (Visit 5 and 8) (for subjects  $\geq 12$  years of age)
- QOLIE-31-P (for subjects  $\geq 18$  years of age)/PedsQL (for subjects  $< 18$  years of age) (Visit 5 and 8 only)
- Achenbach CBCL for subjects  $< 18$  years of age (Visit 5 and 8 only)
- BRIEF for subjects  $< 18$  years of age (Visit 5 and 8 only)
- Healthcare resource use
- Work/school days lost due to epilepsy
- Days with help from a caregiver due to epilepsy

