#### **10.1.4 Pregnancy**

If an investigator is notified that a subject has become pregnant after the first intake of any IMP, the investigator must immediately notify UCB's PS department by providing the completed Pregnancy Report and Outcome form (for contact details see Serious Adverse Event reporting information at the beginning of this protocol). The subject should be withdrawn from the study as soon as pregnancy is known (by positive pregnancy test), and the following should be completed:

- The subject should return for an ET visit.
- The subject should immediately stop the intake of the IMP or be down-titrated as instructed at the ET visit.
- A Safety Follow-Up Visit should be scheduled 2 weeks after the subject has discontinued her IMP.

The investigator must inform the subject of information currently known about potential risks and about available treatment alternatives.

The pregnancy will be documented on the Pregnancy Report and Outcome form provided to the investigator. The progression of the pregnancy and the eventual birth (if applicable) must be followed up using the Pregnancy Report and Outcome form in which the investigator has to report on the health of the mother and of the child. Every reasonable attempt should be made to follow the health of the child for 30 days after birth for any significant medical issues. In certain circumstances, UCB may request that follow up is continued for a period longer than 30 days. If the subject is lost to follow up and/or refuses to give information, written documentation of attempts to contact the subject needs to be provided by the investigator and filed at the site. UCB's PS department is the primary contact for any questions related to the data collection for the pregnancy, eventual birth, and follow up.

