### 10.3 Laboratory measurements

Blood and urine specimens for routine assay of hematology, clinical chemistry, and urinalysis parameters will be collected according to the schedule of study assessments in [Table 5-1](#), [Table 5-2](#), [Table 5-3](#) and [Table 5-4](#). A central laboratory will perform the routine analysis of blood and urine specimens. Pregnancy testing will also be performed (see Section [10.3.2](#)). The procedures for handling and shipping these specimens will be provided to the sites.

The laboratory tests to be performed are presented in [Table 10-2](#).

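### A Baseline failure of childbearing potential can take her first lacosamide dose before any current pregnancy result is required, because the on-site urine test at Visit 1 is optional

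*Protocol*

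**What the plan says.** Section 8.1.1 requires a full Visit 1 for Baseline failures. That list includes a serum pregnancy test for women of childbearing potential, a check of the withdrawal criteria, and dispensing of LCM. Table 5-1 footnote q confirms that the scheduled Visit 1 test is serum. Both places then add: "Baseline failures from SP0982 may have an additional urine pregnancy test at V1 of EP0012, at the investigator's discretion".

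Section 7.2.1 sets the start of treatment at the same visit: "Subjects who are eligible Baseline failures from SP0982 will start at Visit 1 on a dose of LCM 2mg/kg/day" for children under 50kg, and 100mg/day for adults and heavier children.

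Section 10.3 states: "A central laboratory will perform the routine analysis of blood and urine specimens". It mentions pregnancy testing separately and points to 10.3.2, which names no laboratory.

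None of the four exclusion criteria in 6.2 names pregnancy. Section 6.3 item 3 makes it a mandatory withdrawal: "The subject becomes pregnant, as evidenced by a positive pregnancy test".

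**The concern.** Baseline failures were not randomized in SP0982, so Visit 1 of EP0012 can be their first exposure to LCM. The protocol treats pregnancy as incompatible with staying on treatment, yet it does not ask for the answer before treatment begins.

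If a positive serum result arrives after dosing, 10.1.4 calls for an ET visit, and "The subject should immediately stop the intake of the IMP or be down-titrated as instructed at the ET visit". It also calls for a Safety Follow-Up Visit 2 weeks after stopping, and for reasonable attempts to follow the child to 30 days after birth. The woman would also be in the Safety Set, since 12.1.2 requires only one dose. A dipstick read before dispensing avoids all of this for every pregnancy it detects.

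The same gap applies to any subject in the Other category of 5.1 who is not already on LCM. The sentence on the optional urine test does not mention that category.

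**Working it through.** The plan gives no figure to reproduce. The question is the order of events, followed by a short illustration of size.

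**Order of events for a Baseline failure of childbearing potential**

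1. Serum sample: drawn at Visit 1 (8.1.1; Table 5-1 footnote q).
2. Urine dipstick: may be done at Visit 1, if the investigator chooses (same places).
3. Check of withdrawal criteria: done at Visit 1 (8.1.1). Item 3 of 6.3 acts on a positive test, so it cannot act on a result that is still pending.
4. Dispensing and start of LCM: Visit 1 (8.1.1; 7.2.1).
5. A rule that step 4 waits for a negative result from step 1 or 2: none in 5.2, 6.1 to 6.3, 7.2.1, 8.1.1 or 10.3.
6. Next scheduled pregnancy test: Visit 2. Section 8.1.2 lists "Visit 2, 5, and 8 only], and a urine pregnancy test [for women of childbearing potential"; the visit restriction belongs to the laboratory panel, and Table 5-1 marks a pregnancy test at Visit 2. Footnote c adds: "A window of ±7 days relative to Visit 1 is applicable for all visits and telephone contacts". Week 2 is Day 14, so Visit 2 falls between Day 14 − 7 = Day 7 and Day 14 + 7 = Day 21. That is after the first dose in every case.

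A site can therefore do everything required and still start LCM with the pregnancy result unknown.

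**Exposure before the serum result**

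Inputs: 2 doses per day (7.2) and starting doses of 100mg/day or 2mg/kg/day (7.2.1). The turnaround time is not in the document; 1 to 5 days is assumed.

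- Doses = 2 × days: 2 × 1 = 2, up to 2 × 5 = 10.
- Tablets: 100mg/day × 1 = 100mg, up to 100mg/day × 5 = 500mg.
- Oral solution: 2mg/kg/day × 1 = 2mg/kg, up to 2mg/kg/day × 5 = 10mg/kg.
- If the result is available before dispensing on the same day, the exposure is zero.

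The dose does not rise within this range, because 7.2.1 holds Baseline failures at the starting dose through Week 1.

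**The case against.** The best case for the present text has four parts.

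**EP0012 leans on SP0982 eligibility.** Section 5.1 defines a Baseline failure as someone who met every SP0982 entry criterion except the seizure minimum. Inclusion criterion 2 requires that status, and exclusion criterion 2 bars anyone meeting SP0982's withdrawal criteria. These routes may well bar a woman already known to be pregnant; the SP0982 protocol is not available to confirm it. This stands, and it means that the lack of a pregnancy criterion in 6.2 must not be read as permission to enrol pregnant women. It does not supply a current test result at EP0012 Visit 1.

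**The serum test is mandatory, and its delay is not documented.** This also stands. The gap is in when the result is known, not in whether a test is done. A reader might infer from 10.3 that the sample goes to the central laboratory and returns days later. The text does not say so for the serum pregnancy test, so a late result is a possibility, not a stated fact.

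**Other safeguards exist.** Section 7.8.1 says: "Female subjects not surgically sterile or 2 years postmenopausal should practice 1 highly effective method of contraception", unless sexually abstinent. Withdrawal criteria are checked at Visit 1, a urine test follows at Visit 2, and Other subjects need Study Physician approval under 6.1. These lower the chance or the duration of exposure. None requires a negative result before the first dose.

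**The choice was deliberate.** Amendment 2 set out to clarify pregnancy testing and added the urine test as optional. Sites may already do what is proposed here. That makes it a design choice rather than an oversight, but the text gives no criterion for using the discretion.

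**Conclusion.** The concern holds as a limited, avoidable safety gap. The protocol requires a test at Visit 1 but not a result before the first dose, and it leaves the one test that could give an immediate answer to choice. It matters only where the serum result is not back on the day of dispensing.

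The size cannot be fixed from the document. It gives no count of Baseline failures or Other subjects of childbearing potential and no pregnancy frequency. Under the assumed 1 to 5 days, exposure is 2 to 10 starting-level doses per affected woman.

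A reader might infer exposure lasting until Visit 2 with dose escalation in between. That needs the mandatory serum result to be overlooked, which nothing in the document suggests. Nor does a milligram total measure harm to a fetus; the protocol offers no evidence on that, and none is claimed here. The case for change rests on how little the correction asks.

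**What to change.** 1. In 8.1.1 and Table 5-1 footnote q, make the Visit 1 urine pregnancy test mandatory, with a negative result before LCM is dispensed, for Baseline failures of childbearing potential and for any Other subject of childbearing potential not already on LCM.
2. Keep the Visit 1 serum sample, since a dipstick can miss a very early pregnancy.
3. Add a positive pregnancy test to 6.2 for subjects who will receive LCM. Subjects entering only for Safety Follow-Up are then unaffected, and 6.3 item 3 continues to cover later positive results.

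The cost is a change of wording and one dipstick per affected subject. The test is already permitted at Visit 1 and scheduled at Visit 2, so sites need the supplies anyway.
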